12.3 SAMPLE SIZE DETERMINATION

Based on the study by Alekseichuk et al 2017 which investigated the effect of CF-tACS on task accuracy and resting state EEG connectivity in 20 healthy participants per crossover arm, we conjecture that our effect size is at least 0.48. With this effect size, our sample size of 24 has power greater than 60% with alpha 0.05. We have improved upon the experimental design in Alekseichuk et al 2017 by personalizing our stimulation frequencies to target the frequencies of peak phase-amplitude coupling during the task. With this methodological improvement, we expect our effect size to increase to 0.6 (see Romei et al. 2016). With this effect size, our sample size has power greater than 85%.

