7 STUDY OUTCOMES

7.1 PRIMARY OUTCOMES

The cognitive task will consist of 400 trials. The EEG recorded simultaneously with the task will be analyzed following an established preprocessing pipeline to remove artifacts related to eye movements, eye blinks, heart beats and muscle activity. The oscillation power and phase will be estimated using Morlet wavelet convolution. The primary outcome is phase-amplitude coupling between the stimulated frequencies (measured from EEG), reaction time, and accuracy. Phase amplitude coupling will be calculated using the phase locking value z-corrected based on a boot-strapped null distribution from randomly shifting the amplitude values 1000 times (see Cohen *Analyzing Neural Time Series Data* 2014 for method).

Our primary outcomes:

- Theta-gamma tACS will increase theta-gamma phase amplitude coupling (one-tailed, Student's t-test)
- Delta-beta tACS will increase delta-beta phase amplitude coupling (one-tailed, Student's t-test).
- Theta-gamma tACS will alter behavior (reaction time or accuracy) as a function of set-size (Student's t-test).
- Delta-beta tACS will alter behavior (reaction time or accuracy) as a function of abstraction (Student's t-test).

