12.1 STUDY HYPOTHESIS

NULL HYPOTHESIS. The change in task-performance for the cognitive control task is not significantly modulated by CF-tACS relative to sham tACS.

ALTERNATIVE HYPOTHESIS. CF-tACS induces an enhancement in task-performance during the cognitive control task by increase phase-amplitude coupling. This enhancement in performance is frequency specific. Theta-gamma CF-tACS modulates performance as a function set-size. Delta-beta CF-tACS modulates performance as a function of abstraction.

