12.2 STATISTICAL ANALYSIS PLANS

Statistical analyses will be performed to test the null hypothesis indicated in section 2.4 *Study Aims/Hypothesis*.

The cognitive task will consist of 400 trials. The EEG recorded simultaneously with the task will be analyzed following an established preprocessing pipeline to remove artifacts related to eye movements, eye blinks, heart beats and muscle activity. The oscillation power and phase will be estimated using Morlet wavelet convolution. The primary outcome is phase-amplitude coupling between the stimulated frequencies (measured from EEG), reaction time, and accuracy. Phase amplitude coupling will be calculated as the phase locking value corrected for spurious noise using a boot-strapped null distribution (see Cohen Analyzing Neural Time Series Data 2014 for method).

Our primary outcomes and their test are described below:

- Theta-gamma tACS will increase theta-gamma phase amplitude coupling (one-tailed, Student's t-test)
- Delta-beta tACS will increase delta-beta phase amplitude coupling (one-tailed, Student's t-test).
- Theta-gamma tACS will alter behavior (reaction time or accuracy) as a function of set-size relative to sham-tACS (Student's t-test).
- Delta-beta tACS will alter behavior (reaction time or accuracy) as a function of abstraction relative to sham-tACS (Student's t-test).

As exploratory analysis, linear mixed-effects models with BDNF genotype, sex hormone levels, as factors in addition to the variables condition and period will be fit with the rest of the analysis following what is described for primary analysis.

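### The null in 12.1 concerns overall task performance, but the behavioural primary tests are demand-specific contrasts, and 12.3 does not say which outcome or contrast its power applies to

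*Combined protocol and SAP*

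**What the plan says.** Section 12.1 gives the only null hypothesis in the document: "The change in task-performance for the cognitive control task is not significantly modulated by CF-tACS relative to sham tACS". It names no demand factor. The alternative in the same section begins with a general enhancement of performance. It then makes the effect frequency-specific, with theta-gamma stimulation acting through set-size and delta-beta stimulation through abstraction.

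Section 12.2 says "Statistical analyses will be performed to test the null hypothesis indicated in section 2.4", but section 2.4 contains three aims and no null, so 12.1 is the only candidate.

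Sections 7.1 and 12.2 list four primary tests. Two are one-tailed tests of phase-amplitude coupling with no demand factor. The other two are behavioural, for example "Theta-gamma tACS will alter behavior (reaction time or accuracy) as a function of set-size relative to sham-tACS (Student's t-test" in 12.2 and "Delta-beta tACS will alter behavior (reaction time or accuracy) as a function of abstraction (Student's t-test" in 7.1. Neither behavioural test is labelled one-tailed.

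The secondary outcomes in 7.2 are two brain-behaviour correlations, both to be run only for behavioural results that reach significance. The exploratory mixed model in 12.2 includes condition and period. It names no behavioural outcome, and 7.3 links the genotype and hormone covariates to spectral power.

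Section 12.3 bases the sample size on a study "which investigated the effect of CF-tACS on task accuracy and resting state EEG connectivity in 20 healthy participants per crossover arm" and continues "we conjecture that our effect size is at least 0.48". It says "our sample size of 24 has power greater than 60% with alpha 0.05". Citing a second source for personalised frequencies, it adds "we expect our effect size to increase to 0.6", with power then put above 85%.

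**The concern.** The hypothesis to be tested and the tests that are written are different quantities. A test of whether the verum-sham difference changes with set-size or abstraction is a difference of differences. It carries no information about an effect that is the same at every level. If a regimen shifts reaction time or accuracy equally across levels, the 12.1 null is false, but the behavioural tests reject only at their false-positive rate. The correlations in 7.2 would then not be run either, because they are conditional on a significant behavioural finding. The pilot could report no behavioural effect when there is one. The overall effect on performance, a natural planning quantity under Aim 3, would have no pre-specified estimate.

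The power statement has a related gap. A standardised effect for a simple verum-sham difference is not the standardised effect for an interaction contrast, so the printed power cannot be read across to the behavioural tests.

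**Working it through.** **Inputs.** From 12.3: n = 24, alpha 0.05, effect sizes 0.48 and 0.6, and power above 60% and above 85%. Sidedness, outcome, contrast and standardiser are not stated. From section 4: a within-person crossover, so comparisons are paired. From 4.1.2: dropouts are left out of the analysis and their codes reused, so I take 24 completers.

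**Step 1: reproduce the printed power.** For a paired t-test with standardised mean difference d, power comes from the noncentral t with 23 degrees of freedom and noncentrality d × √24. This is 0.48 × 4.899 = 2.35 and 0.6 × 4.899 = 2.94.

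| d | two-sided 5% | one-sided 5% | printed |
|---|---|---|---|
| 0.48 | 61.5% | 73.8% | above 60% |
| 0.6 | 80.4% | 88.6% | above 85% |

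The normal approximation, two-sided, gives 65.2% and 83.6%. A two-sample test with 24 per arm gives 37.0% and 53.0% and does not fit. The figures therefore fit a simple paired difference, and both inequalities hold together only one-sided.

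**Step 2: relate the interaction test to the overall effect.** Assume two demand levels. Let the verum-sham differences have SD 1 at each level and correlation ρ, with mean h at high demand and f × h at low demand.

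- Overall effect: d_overall = [h(1 + f)/2] / √[(1 + ρ)/2]
- Interaction effect: d_int = h(1 − f) / √[2(1 − ρ)]
- Ratio: d_int / d_overall = [(1 − f)/(1 + f)] × √[(1 + ρ)/(1 − ρ)]

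The documents give neither f nor ρ, so both are varied below.

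**Step 3: power of the interaction test, two-sided 5%, n = 24.**

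| Low-demand effect as share of high | ρ | overall d = 0.48 | overall d = 0.6 |
|---|---|---|---|
| equal (f = 1) | any | 5.0% | 5.0% |
| half (f = 0.5) | 0 | 11.7% | 15.6% |
| half (f = 0.5) | 0.5 | 25.6% | 36.9% |
| half (f = 0.5) | 0.7 | 43.2% | 60.8% |
| none (f = 0) | 0 | 61.5% | 80.4% |
| none (f = 0) | 0.5 | 97.4% | 99.8% |

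Worked case, f = 0.5 and ρ = 0.5: the ratio is (0.5/1.5) × √3 = 0.577, so d_int = 0.6 × 0.577 = 0.346 and power is 36.9%. Simulation with 40,000 runs at ρ of 0 and 0.5 agrees (for example 37.1% for this case, and 4.8% to 5.0% for the uniform effect).

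**Step 4: when does the interaction test match the overall test?** The effect need not be confined to high demand. At ρ = 0.5 and f = 0.25 the ratio is 0.6 × √3 = 1.04, and at d = 0.6 power is 83%. At ρ = 0.7 and f = 0.4 the ratio is 1.02 and power is 82%. Both slightly exceed the 80.4% of the overall test.

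**The case against.** The strongest defence is that the tests match the stated alternative. Section 12.1 goes on to name set-size and abstraction, so the investigators test what they predict, and only the null is worded more broadly. That stands, and it is why the interaction tests should stay. It does not give the stated null a test.

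A reader might infer that 0.48 is an effect on task accuracy and that the sizing was done for a behavioural main effect. The documents do not support this. Section 12.3 names accuracy and EEG connectivity together and attributes 0.48 to neither, and 0.6 rests on a different citation. The two coupling tests are one-tailed simple contrasts, and one-sided is the only reading under which both printed figures hold, so the power may have been meant for them. In that case the behavioural tests have no stated power basis.

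A reader might also infer that an overall effect is never examined and would be found only 5% of the time. Both go too far. The exploratory mixed model includes condition, although whether it covers behaviour is unclear. The 5% applies to an exactly uniform effect and to each test separately. Because either reaction time or accuracy may count, the chance of at least one rejection per regimen could reach 1 − 0.95² = 9.75% if the two are independent, which is still only a false-positive rate.

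Finally, interaction is the natural reading of the behavioural tests, but the plan does not define the statistic. This is also a hypothesis-generating pilot, which limits the weight of any power claim.

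**Conclusion.** The concern holds in a limited form. The 12.1 null on overall performance has no matching primary or secondary test. For an effect equal across demand levels, each behavioural test rejects at about 5%. The power in 12.3 is not tied to an outcome or contrast. It fits a simple paired difference, and the figure above 85% requires a one-sided test (80.4% two-sided), whereas the behavioural tests are not labelled one-tailed.

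The power of the interaction tests cannot be fixed from the documents. Under the two-level, equal-SD model with an overall effect of 0.6, it runs from 5% to above 99% depending on the pattern across levels and the correlation. The plan should correct this before analysis, but it does not invalidate the demand-specific tests.

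**What to change.** In 12.2, add for each active regimen a pre-specified secondary verum-minus-sham contrast in reaction time and in accuracy, averaged over demand levels, with a 95% CI. Name it as the test of the 12.1 null, and correct the pointer to section 2.4. Keep the interaction tests as the frequency-specific hypotheses and define their statistic.

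In 12.3, state which outcome and contrast 0.48 and 0.6 refer to. Limit the printed power to a simple paired verum-sham difference and give its sidedness (80.4% two-sided at 0.6). For the interaction tests, give a power range under stated assumptions about the low-demand share and the between-level correlation, or give the detectable effect. By the same paired-t calculation, n = 24 has about 80% two-sided power for an interaction difference score with a standardised mean of about 0.6.

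The cost is four secondary contrasts (two regimens by two measures) on data already collected and a less favourable power statement. No extra participants or visits are needed.

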13 DATA HANDLING AND RECORD KEEPING

The study coordinator and research assistants are responsible for the accuracy, completeness, legibility, and timeliness of the data reported.

13.1 PHI AND HIPAA

Information about study participants will be kept confidential and managed according to the requirements of the Health Insurance Portability and Accountability Act of 1996 (HIPAA). Those regulations require a signed subject authorization informing the subject of the following:

- What protected health information (PHI) will be collected from the participants in this study
- Who will have access to that information and why
- Who will use or disclose that information
- The rights of a research subject to revoke their authorization for use of their PHI.

In the event that a participant revokes authorization to collect or use PHI, the investigator, by regulation, retains the ability to use all information collected prior to the revocation of participant authorization. For participants that have revoked authorization to collect or use PHI, attempts should be made to obtain permission to collect at least vital status (i.e., that the subject is alive) at the end of their scheduled study period.

13.2 CONFIDENTIALITY

Data will be stored in a password-protected cloud-based data system that meets UNC IT Data Security requirements at the level determined by the IRB. Individual records are referred to by dummy identifiers that cannot be traced back to the study participants except with the master code list that is stored separately in a secured location. Source documents (i.e. paper forms) will be kept in a locked file cabinet in a locked office. The key linking dummy identifiers with participant information will be securely located separate from all other data collected, and will never appear in an electronic format.

13.2.1 ACCESS TO SOURCE DOCUMENTS

The research coordinator, research assistants, and PI will have access to all of the source documents collected over the course of the study.

Data will stay on a password-protected computer. Subsequently, a copy will be processed on a separate, password-protected desktop computer in the [name] Lab ([name]).

13.2.2 SENSITIVE INFORMATION

Sensitive information may be collected during the screening process in order to determine eligibility (medical history, recreational drug use, etc.). Such information will be de-identified and stored in a secure, locked file cabinet, and will not be used in any further proceedings in the study.

13.2.3 OTHER

Please note that there is no significant risk of deductive disclosure in this study. In addition, none of the groupings or subgroupings used in analysis will be small enough to allow individuals to be identified.

13.3 SOURCE DOCUMENTS

Source data is all information, original records of clinical findings, observations, or other activities in a clinical trial necessary for the reconstruction and evaluation of the trial. Source data are contained in source documents.

Source data include:

UNC HUMAN RESEARCH COMMITTEE (IRB).

- All IRB correspondences are documented
- The study staff is IRB approved prior to performing any study procedures
- Adverse events and deviations are reported to the IRB per current guidelines and stored appropriately
- All versions of the IRB protocols and informed consent forms are on file

INFORMED CONSENT.

- Ensure that participant identification is not recorded on the ICF (i.e., no participant ID)
- There is documentation that the participant is given a copy of the consent form
- The participant and study representative signed and dated the consent form for him/herself
- The participant initialed and dated all appropriate pages on the informed consent form
- Note to file (Appendix F) made for any informed consent deviations
- Ensure a valid (current version date) copy of the consent form was used

PROTOCOL DEVIATIONS.

- Any and all protocol deviations (exceptions and violations) are documented in the participant folder and reported to the IRB as required

OTHER SOURCE DOCUMENTS.

- Each participant folder will contain a checklist to ensure that all source documents are administered and collected properly. The checklist will be dated by the researcher for each time an assessment is administered
- Review participant folders to ensure the accuracy, completeness, and legibility of the data.
- Any correction made to the source documents is dated, initialed, and explained. The original entry should not be obscured.
- The protocol-specific source documents are on file.
- Source documents are completed in ink.
- Note to files (Appendix F) are made for missing or incomplete data and to explain any discrepancies or additional comments.

DNA.

- Participant names will not be on any of the samples collected. DNA is sequenced to check for one nucleotide. When testing is performed, only de-identified information is shared with an outside party. This information will not be shared with anyone outside of the study personnel, including the participant.

Hormone Levels

- Participant names will not be on any of the samples collected. Saliva is collected to assess for sex hormones estradiol, progesterone and testosterone. When testing is performed, only de-identified

information is shared with an outside party. This information will not be shared with anyone outside of the study personnel, including the participant.

13.4 DATA MANAGEMENT RESPONSIBILITIES

The responsibilities designated to each member of the research team are documented on the Delegation of Authority Form. The study coordinator and research assistants will be responsible for the informed consent process, review for eligibility, questionnaire administration, data entry, device administration, and CRF entries. The study coordinator will be responsible for AE/SAE documentation and reporting, while the PI will be responsible for the AE assessment, review of the AE documentation forms, and overview of the research staff.

13.5 DATA CAPTURE METHODS

Data will be entered directly from the source documents and stored on a password-protected computer in the [name] Lab by a researcher. All stored data will be de-identified and will not contain any reference to participant name or other personal information, such as email or phone number.

13.6 PROTOCOL DEVIATIONS

All deviations from the protocol will be addressed in study participant source documents. The researcher will complete a Protocol Deviation Log using the participant code as the identifier. This form will collect information such as the date the deviation occurred, details of what the deviation consisted of, any corrective and preventative actions that were taken as a result of the deviation, and the date that the PI and IRB were notified. The PI will review the information and initial once approved. A completed copy of the Protocol Deviation Form will be maintained in the regulatory file, as well as in the participant's source document. Protocol deviations will be sent to the IRB per their guidelines. The site PI/study staff will be responsible for knowing and adhering to their IRB requirements.

13.7 RECORD RETENTION

According to the University of North Carolina at Chapel Hill's Archives and Record Management Services schedule for General Records Retention and Disposition Schedule 6.10, records will be kept for 5 years after the completion of the study or grant end date, whichever is later.

14 ETHICAL CONSIDERATIONS

14.1 ETHICAL STANDARD

The investigator will ensure that this study is conducted in full conformity with the principles set forth in the Belmont Report: Ethical Principles and Guidelines for the Protection of Human Subjects of Research, as drafted by the US National Commission for the Protection of Human Subjects of Biomedical and Behavioral Research (April 18, 1979) and codified in 45 CFR Part 46 and/or the ICH E6; 62 Federal Regulations 25691 (1997).

14.2 INSTITUTIONAL REVIEW BOARD (IRB)

The Office of Human Research Ethics is responsible for ethical and regulatory oversight of research at UNC-Chapel Hill that involves human participants. The OHRE administers, supports, and guides the work of the Institutional Review Boards and all related activities. Any research involving human participants proposed by faculty, staff, or students must be reviewed and approved by an IRB before research may begin, and before related grants may be funded. OHRE and the IRBs are critical components of the coordinated Human Research Protection Program, which serves to protect the rights and welfare of human participants. All components of this program must work together to ensure institutional compliance with ethical principles and regulatory requirements. The following is a mission statement for the coordinated Human Research Protection Program:

The University of North Carolina at Chapel Hill is committed to expanding and disseminating knowledge for the benefit of the people of North Carolina and the world. An important part of that commitment to knowledge is research of the highest quality on all aspects of the health and behavior of people, and such research is only possible through the participation of humans as research participants. Human participants are partners in research and a precious resource to the university. At UNC-Chapel Hill, human participant research is a privilege, but not a right. Consistent with that philosophy, it is the mission of the UNC-Chapel Hill Human Research Protection Program to ensure that:

- a. The rights and welfare of human participants are paramount in the research process;
- b. The highest standards of ethical conduct are employed in all research involving human participants;
- c. Research investigators are properly trained in the ethical and regulatory aspects of research with human participants;
- d. Research investigators deal honestly and fairly with human participants, informing them fully of procedures to be followed, and the risks and benefits of participating in research; and
- e. Research using human participants at UNC-CH conforms to applicable local, state, and federal laws and regulations and the policies of the university.

14.3 INFORMED CONSENT PROCESS

Informed consent is a process that is initiated prior to the individual's agreeing to participate in the study and continues throughout the individual's study participation. Extensive discussion of risks and possible benefits of tACS will be provided to the participants. Consent forms describing, in detail, the study intervention, device, procedures, and risks are given to the participant and written documentation of informed consent is required prior to the administration of any treatment or assessments used in this study. All consent forms will be IRB-approved and updated with any new information as modifications are made throughout the study.

The researcher and potential participants will review the clinical trial in its entirety by reviewing the consent form together in a private location. If the participant is unclear on any part of the consent form, the research will return

to the section and explain further. Participants must sign the informed consent document prior to any procedures taking place. Participants may withdraw consent at any time throughout the course of the trial. A copy of the informed consent document will be given to the participants for their records.

